This study proposes to evaluate a new indication for JUVÉDERM VOLUMA™ XC, for which the benefit/risk profile has not been entirely assessed. While the risks of stroke and blindness may be small, the jawline and cheek are highly vascularized areas. Due to limited experience and research associated with dermal filler use in this area, the actual risk is unknown.

Alternatives

Alternatives to treatment include but are not limited to other injectable fillers, surgical implants, and surgery.

Study Purpose and Objectives

Purpose:

The purpose of this clinical investigation is to study the perceived reduction of jowling following a volume replacement treatment using JUVÉDERM VOLUMA™ XC in the jawline or in the jawline and the cheek

Primary Objective:

The primary objective of this study is to see that a clinically relevant jowl improvement can be achieved with hyaluronic acid filler into the jawline and/or cheek (Endpoint #1).

The secondary objective is to determine which of the 2 methods (jowl injection alone or jowl injection with cheek injection) is superior (Endpoint #2).

Study Design

Scope:

The clinical study will include 16 patients at one clinical site.

Duration:

Eligible patients will receive 1 treatment according to the study protocol, and will be followed for a period of 12 months to document safety and efficacy. Patient and/or doctor may choose to have a touchup at 1 month. All subjects will be followed for 12 months from the time of the last injection session.

Patient Selection

Each patient will be evaluated by the Investigator to assess his or her suitability for entry into the study.

- 1. Jowling grade 2-3 by the Lower Face Jawline at Rest Scale (1), by both MD evaluator and patient.
- 2. Female patients must not be pregnant or trying to get pregnant and must have negative urine pregnancy tests before treatment.
- 3. Non-pregnant females ages 35-65 in good general health.
- 4. A study participant must be able to give proper informed consent in writing and be willing to follow the treatment schedule and undertake to carry out all necessary precautions and instructions.
- 5. Able to participate in telemedicine video visits.
- 6. Able to understand the requirements of the study and willing and able to follow all study procedures and attend all study visits, and successfully complete the study.

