Photographs will remain unretouched. One blinded dermatologist and one unblinded dermatologist will rate the patient's severity of jowling based on the Jawline Rating Scale (JRS) (1) at baseline, the 4-week, 8-week, and 12 or 16-week visits. The patient will also rate their jowling based on the JRS as well as their satisfaction with the procedure.

Analysis of Scientific Soundness of the Protocol

The proposed study has been designed to provide a valid method to analyze the safety and efficacy of facial volume replacement. Measure taken to assure that the study provides valid data are as follows:

- 1. Photographs will be taken under standardized conditions. Photographs will be taken with a VISIA CR, a device made by Canfield Scientific specifically to be utilized for clinical research to provide uniformity in patient photographs.
- 2. Adverse or unanticipated effects that occur during the course of this clinical study will be recorded and carefully analyzed as to their relationship to the treatment.
- 3. Evaluators will review individual photos without knowledge of if they are before or after photos.

Primary Outcome Measure:

The primary outcome is a reduction of 1 or more points of the Jawline Rating Scale (JRS)
 Assessment (on scale of 0 to 4) at baseline versus that at 4 weeks from the last injection (whether initial or touch-up) based on any or all of one blinded dermatologist rating, one unblinded dermatologist rating, and patient rating. (A lower number will mean a better outcome) Time Frame: Baseline to 4 weeks after last injection.

Secondary Outcome Measures

- 1. Reduction of 1 or more points of the Jawline Rating Scale (JRS) Assessment (on scale of 0 to 4) at baseline versus that at 4 weeks from the last injection based on the patients rating while looking in the mirror and at before and after photographs. A lower number will mean a better outcome. Time Frame: 4 weeks from last injection
- 2. Whether group 1 and group 2 has a higher reduction in the Jawline Rating Scale (JRS) (on scale of 0 to 4) at 4 weeks from the lastinjection compared to baseline based on ratings from one blinded dermatologist and one unblinded dermatologist. A lower number will mean a better outcome. Time Frame: 4 weeks from last injection

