- 3. Whether group 1 or group 2 has a higher reduction in the Jawline Rating Scale (JRS) (on scale of 0 to 4) at 4 weeks from the last injection compared to baseline based on the patients rating while looking in the mirror and at before and after photographs. A lower number will mean a better outcome. Time Frame: 4 weeks from last injection
- 4. Jawline Rating Scale (JRS) Assessment on scale of 0 to 4 at 4 weeks: One blinded dermatologist and one unblinded dermatologist will rate the patient's severity of jowling based on the Jawline Rating Scale (JRS). The patient will also rate their jowling based on the Jawline Rating Scale (JRS). The scale is on a rating of 0 to 4. A lower number will mean a better outcome. [Time Frame: 4 weeks]
- 5. Jawline Rating Scale (JRS) Assessment on scale of 0 to 4 at 8 weeks: One blinded dermatologist and one unblinded dermatologist will rate the patient's severity of jowling based on the Jawline Rating Scale (JRS). The patient will also rate their jowling based on the Jawline Rating Scale (JRS). The scale is on a rating of 0 to 4. A lower number will mean a better outcome. [Time Frame: 8 weeks]
- 6. Jawline Rating Scale (JRS) Assessment on scale of 0 to 4 at 12 or 16 weeks: One blinded dermatologist and one unblinded dermatologist will rate the patient's severity of jowling based on the Jawline Rating Scale (JRS). The patient will also rate their jowling based on the Jawline Rating Scale (JRS). The scale is on a rating of 0 to 4. A lower number will mean a better outcome. [Time Frame: 3 months from last treatment]
- Incidence of abnormal eye exam (Confrontational Visual Fields Exam) findings (Safety):
 Ophthalmologic exams that include Confrontational Visual Fields Exam will be performed prior to any
 treatment, 30 minutes after treatment, and at all follow up in-person visits. [Time Frame: up to 18
 months]
- 8. Incidence of abnormal eye exam (Snellen Eye Exam) findings (Safety):
 Ophthalmologic exams that include Snellen Eye Exam will be performed prior to any treatment, 30 minutes after treatment, and at all follow up in-person visits. [Time Frame: up to 18 months]
- 9. Incidence of abnormal eye exam (Ocular Motility Exam) findings (Safety):
 Ophthalmologic exams that include Ocular Motility Exam will be performed prior to any treatment,
 30 minutes after treatment, and at all follow up in-person visits. [Time Frame: up to 18 months]

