^{*} Safety Eye Assessments will be performed prior to treatment and 30 minutes after treatment

^{**}Patient diary to be completed daily by email for 30 days following treatment

^{***}No Retreatment done per patient and/or physician

advanced Jowl Improvement with Injectable Fillers: Jawline Injections alone vs Jawline and Cheek Injections

Blinded Physician Assessment

Patient Number	Date:			
Baseline or Date pos Baseline or Date Pos	t 1 st Injection: Baselin st 2 nd Injection: Baselin	e4w8w_ ne4w8w_	12 week 16 12 week 16	16 week sweek
No.	OMAZ -	- CMAZ	CMAZ	SMB2
OMerz O	- OMerz	CMerz CMerz	GMerz S	©Merz.
0	1	2	3	4
No sagging	Mild sagging	Moderate sagging	Severe sagging	Very severe sagging
pictured above, put a	etructions: Without reference X by the value you 3 4	feel represents the a		
the patient prior to in	jection and the photogoutting an X by the varied	graph of the patient to	oday, please evaluate	
Comments:				
Blinded Physician: Date:	Name	Sig	nature	

advanced Jowl Improvement with Injectable Fillers: Jawline Injections alone vs Jawline and Cheek Injections 10001

Subject Self-Assessment of Results

Patient Number				
Date:				
Baseline or Date post Or: Date Post 2 nd Injection	-	line 4 w 8 8w 12 w_		16 week
©Merz ©Merz	OMerz	SMerz	CMerz CMerz	CMerz CMerz
3	1	1	3	1
0	1	2	3	4
No sagging	Mild sagging	Moderate sagging	Severe sagging	Very severe sagging
Grading of Jowls Instructured above, put an				
1 2	34	_ 5		
Grading of Jowls by p yourself prior to inject putting an X by the va	ion and the photogra	ph of yourself today, p	olease evaluate your	
Much improved Improved No change Worse Much Worse	-			
Comments:				
Signature of Coordi	nator	Date:		

	Iowl/Jawline Study Iumber	10001-Patient Diary		Date
	e treatment			
many da	ys it has been since	= :	ne questions v	patient number, the date, and how which require to answer mild,
• N	Moderate: minimal,	and/or local or noninva out not immediately life	sive intervent	only; no intervention needed tion needed nospitalization or prolongation of
Have y	you experien	ced any of the fo	ollowing s	symptoms?
	oderate to Severe Di yes was it Mild	zziness Moderate		NO
	onfusion yes was it Mild	Moderate		NO
		s in your arms or legs Moderate		
	nanges to consciousn yes was it Mild	ess or alertness Moderate		NO
		eech impairment Moderate		
If		Moderate	Severe	
				bove questions, pleas
 1811 91 2 2 2 2 2 2 2 2 2 2 2 2 2 2 2 2 2 	L1 and seek i	mmediate medi	cal attent	ion.

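### Secondary outcomes 1 and 3 have the patient grade jowling with before and after photographs in view, which is impossible at baseline and does not match the subject form

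*Combined protocol and SAP*

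**What the plan says.** Secondary Outcome Measures, item 1, counts a patient as improved when the JRS (0 to 4, lower is better) falls by at least one point, comparing the score "at baseline versus that at 4 weeks from the last injection based on the patients rating". The viewing condition is part of that definition: the change is "based on the patients rating while looking in the mirror and at before and after photographs". Item 3 compares the two groups on the same self-rating, "compared to baseline based on the patients rating while looking in the mirror and at before and after photographs".

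The Primary Outcome Measure uses the same one-point threshold at the same time, judged on "any or all of one blinded dermatologist rating, one unblinded dermatologist rating, and patient rating". Neither it nor secondary outcomes 4 to 6, which also use the patient's JRS rating, gives a viewing condition.

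The patient must already have a grade before treatment. Patient Selection, item 1, requires "Jowling grade 2-3 by the Lower Face Jawline at Rest Scale (1), by both MD evaluator and patient".

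The form headed "Subject Self-Assessment of Results" has boxes for baseline and follow-up. It prints two items in this order: a numeric grade against the pictured scale, and a comparison of the pre-injection photograph with today's, answered on five levels from much improved to much worse.

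**The concern.** A change score is interpretable when both measurements are made in the same way. At baseline the patient can use the mirror and at most a before photograph. At week 4, on the wording of outcomes 1 and 3, she has a known before and after pair in front of her while choosing a severity grade. The grade may then become a judgement of change expressed on a severity scale.

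The plan guards against this for others: under Analysis of Scientific Soundness of the Protocol, item 3, evaluators see single photographs without being told which are before and which after. No such safeguard is stated for patients. They cannot be masked to having been treated, but the photograph pair is a separate cue and can be removed.

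Both groups receive filler and there is no untreated control, so nothing in the design subtracts a measurement shift from the within-patient change. The threshold is a single grade and the sample is 16.

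**Working it through.** The plan gives no response rate, rating error or power figure, so there is no stated figure to reproduce. The check sets the passages side by side and then looks at what a shift would do.

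**1. Baseline condition.** The entry criterion needs a patient grade before treatment. It names the scale differently from the outcome section, but both cite reference 1, so I treat them as the same scale. Appendix 1 places the patient evaluation at screening and first ticks photography at the treatment visit; Pre-Procedure Evaluation also mentions pre-treatment photographs at enrolment. On either reading no after photograph can exist.

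**2. Follow-up condition.**

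| Place | Patient's JRS at week 4 |
|---|---|
| Secondary outcomes 1 and 3 | Mirror plus before and after photographs |
| Secondary outcome 4 | No viewing condition |
| Primary outcome | No viewing condition |
| Subject form | Numeric grade first; photograph pair in a separate item |

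The same week-4 self-grade is thus tied to photographs in outcome 1 and not in outcome 4, and the primary outcome does not say which one it uses.

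**3. Where a shift would go.** Let D be a group's true mean reduction and s the part of the recorded reduction due only to the change in viewing condition.

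- Within patients: recorded reduction = D + s. Nothing removes s.
- Between groups: recorded difference = (D2 + s2) − (D1 + s1) = (D2 − D1) + (s2 − s1). If s is the same in both groups it cancels, apart from floor effects at grade 0.

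**4. Weight of one patient.** N = 16 (Study Design, Scope), so one reclassified patient moves the overall responder rate by 1/16 = 6.25 points. With 1:1 allocation, 8 per group, it moves a group's rate by 1/8 = 12.5 points.

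**5. Illustration only.** A simulation (2,000,000 draws) assumed no true change, a latent grade uniform on 0.5 to 4.5, and a rated grade equal to the latent grade plus normal error, rounded. Entry was restricted to a rated grade of 2 or 3. The follow-up rating was shifted downwards by s. Apart from the 2-3 entry range, none of these inputs comes from the documents, and the sign of s is assumed.

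| Shift s (points) | False responders, error SD 0.3 | False responders, error SD 0.5 |
|---|---|---|
| 0 | 17% (2.7 of 16) | 26% (4.1 of 16) |
| 0.25 | 32% (5.1 of 16) | 37% (5.9 of 16) |
| 0.5 | 50% (8.0 of 16) | 50% (8.0 of 16) |
| 1.0 | 83% (13.3 of 16) | 74% (11.9 of 16) |

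The first row is rating error alone. The increase down each column is the effect of the assumed shift; a shift the other way would lower the rate. The table shows that a one-grade threshold is sensitive to a modest shift, not that such a shift occurs.

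**The case against.** The best defence is the form. It already separates the numeric grade from the photograph comparison and prints the grade first. On that reading the outcome wording is a loose summary of both items, and the JRS grade may never be given with the photographs in view. The form's grading instruction is broken in the text available here. The parallel item on the blinded physician form tells the rater to grade without reference to something; if the subject form carries the same words, practice at the visit is already right. Text lost this way cannot be held against the plan.

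This stands as far as it goes: the documents do not establish that patients grade the JRS while viewing the pair. But outcomes 1 and 3 define what is analysed, and they say something different from the form. A further reading, that the patient grades both photographs in one sitting, would equalise the conditions. It fits poorly with the baseline box and the entry grade, and would still be an unmasked side-by-side judgement.

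A reader might also infer that the self-rated change is biased in favour of treatment. The documents do not support that. Standardised, unretouched photographs could prompt a lower grade, or could correct an optimistic impression from the mirror.

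Nor do they show that outcome 3 is seriously compromised, since both groups are rated under the same wording. Equal shifts are not guaranteed: no patient masking is described, and the groups differ in injection sites and syringe totals (1-2 against 2-5). Even so, nothing in the documents points to a difference in either direction.

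Finally, the reach into the primary outcome is conditional. It depends on whether the any-or-all wording lets a patient rating suffice alone, and on whether that rating is the photograph-assisted one.

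**Conclusion.** The point holds as an inconsistency that carries an avoidable risk of bias. Outcomes 1 and 3 name a viewing condition that cannot be met at baseline and that does not match the form. If it is followed, the within-patient self-rated change mixes treatment effect with a change in measurement. Outcome 1 is the most exposed, the primary outcome conditionally so, and outcome 3 least.

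Size and direction are unknown. The only quantities the documents support are 6.25 points per reclassified patient overall and 12.5 within a group; the simulated rates rest on assumed error and shift. It would be wrong to conclude that a given number of responders is spurious. The change is still worth making, because the comparison is uncontrolled, the threshold is one grade, and the remedy is nearly free.

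**What to change.** Reword secondary outcomes 1 and 3 to match the form:

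- The patient records the JRS grade from the mirror only, before any photograph is shown, at baseline and at every visit where it is rated.
- The before and after photographs are then shown and used only for the five-level improvement item, reported as a separate outcome.
- The mirror-only grade is named as the patient rating in the primary outcome and in secondary outcomes 1 and 3 to 6.

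Check the subject form's grading instruction in the source file. If it does not already say that photographs are withheld until the grade is recorded, add that sentence.

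The printed item order already fits, so the cost is a wording change in the protocol and possibly one line on the form. No extra visit, data or staff is needed. If ratings have already been collected, report under which condition they were obtained.

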Many practitioners also use fillers with high G prime along the jawline or lateral face to accomplish improving the jowls. This technique, alternatively called "jawline filler, jawline lift", has not received FDA approval. JUVÉDERM VOLUMA® XC injectable gel is currently FDA approved for deep injection in the cheek area to correct age-related volume loss. In practice, we have seen the advent of cheek treatments with Voluma causing noticeable lifting in the jowls and also the nasolabial fold. However, recent experimentation with filler into the mandible lateral to the jowl, sometimes accompanied by injection into the preauricular area by this author has revealed that this area has been underrepresented in filler solutions for jowling.

Protocol Summary

This study is proposed to evaluate the best protocol for achieving improvement in the sagging jawline.

JUVÉDERM VOLUMA™ XC will be injected in each of 16 women with sagging of grades 1-3 using a published jawline evaluation scale (1).

Patients will be randomized 1:1 into 2 groups:

Patient Group 1: JUVÉDERM VOLUMA™ XC 1-2 syringes (each syringe is 1 cc) will be injected bilaterally into the lateral jawline and inferior cheek area (preauricular area) (the latter area will be added if necessary to achieve visual improvement in jowl attenuation). Total syringes used per person will have a range of 1-2)

Patient Group 2: JUVÉDERM VOLUMA™ XC 1-3 syringes (each syringe is 1 cc) will be injected bilaterally into the lateral cheek (zygomatic) area plus JUVÉDERM VOLUMA™ XC 1-2 syringes (each syringe is 1 cc) will be injected into the lateral jawline and inferior cheek area (preauricular area) (the latter area will be added if necessary to achieve visual improvement in jowl attenuation). Total syringes used per person will have a range of 2-5)

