- c. There may be discomfort / pain / bruising and complete discussion of side effects potentially resulting from the treatment, including possible stroke, blindness and scarring
- d. Transient edema may occur immediately following the treatment.
- e. Erythema and bruising may occur following treatment and last up two weeks or longer.
- f. A full disclosure and written consent will be provided and signed.
- g. If necessary as deemed by patient and/or physician, a touch up may be performed at the 1-month visit.
- h. Evaluations by phone and/or telemedicine will be performed at 72 hours after treatment, 6 and 12 months.
- I. Patients will complete a safety diary daily via email for 30 days following treatments.

If the patient passes all of the inclusion and exclusion criteria for entry into the study the investigator will obtain signed Informed consent, enroll the patient into the study, and record required data on the appropriate study data form. Pre-treatment photographs will be taken.

Treatment

- 1. Photographs will be taken prior to treatment with the VISIA CR system and Fotofinder and with an iPad. Frontal, 45- and 90-degree angle shots at standard illuminations will be taken.
- 2. Patients will be randomized to 2 groups:

Patient Group 1: JUVÉDERM VOLUMA™ XC 1-2 syringes (each syringe is 1 cc) in will be injected bilaterally into the lateral Jawline/lateral medial or and inferior cheek area (preauricular area) (the latter area will be added if necessary to achieve visual improvement in jowl attenuation). Total syringes used per person will have a range of 1-2.

Patient Group 2: JUVÉDERM VOLUMA™ XC 1-3 syringes (each syringe is 1 cc) will be injected bilaterally into the lateral cheek (zygomatic) area plus JUVÉDERM VOLUMA™ XC 1-2 syringes (each syringe is 1 cc) will be injected into the lateral jawline and inferior cheek area (preauricular area) (the latter area will be added if necessary to achieve visual improvement in jowl attenuation). Total syringes used per person will have a range of 2-5.

Note: Based on preclinical studies and a toxicological risk assessment, subjects will be limited to 20 mL of JUVEDERM VOLUMA™XC per 60 kg (130 lbs) body mass per year. This includes any "Touch-up Volume"

3. During treatment cold air will be directed toward the injection sites to reduce discomfort.

- 4. Any complications will be noted at each visit and the patient will complete a diary via email or text every day.

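### Endpoint #2 is meant to identify the superior method, but its only criterion is a larger JRS reduction, with no interval or threshold and no rater given precedence

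*Combined protocol and SAP*

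**What the plan says.** Study Purpose and Objectives sets the secondary objective: to "determine which of the 2 methods (jowl injection alone or jowl injection with cheek injection) is superior (Endpoint #2". It is also the comparison in the trial's title.

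Two entries under Secondary Outcome Measures carry it out. Item 2 asks "Whether group 1 and group 2 has a higher reduction in the Jawline Rating Scale (JRS" from baseline to 4 weeks after the last injection, using "ratings from one blinded dermatologist and one unblinded dermatologist". Item 3 asks the same question "based on the patients rating while looking in the mirror and at before and after photographs".

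The Data Analysis section describes what is collected and who rates when. It gives no summary measure, test, confidence interval, alpha level, minimum between-group difference, or rule for ranking or combining raters. The 1-point figure in the primary outcome defines improvement within a patient; it is not a margin between groups.

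On masking, Analysis of Scientific Soundness, item 3, says "Evaluators will review individual photos without knowledge of if they are before or after photos". The protocol calls one dermatologist blinded and the other unblinded, but does not define blinded in terms of group.

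**The concern.** An objective to determine superiority needs a rule for when the data support that claim. Here the only available rule is that one group's reduction is larger. With 8 patients per group and whole-point grades, two equal methods will usually differ by something, so a bare lead says little.

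The second gap is whose rating counts. Item 2 names both dermatologists without precedence, and item 3 adds the patient. Three ratings can therefore answer one question differently, and the choice among them could be made after the data are seen. One of the two dermatologists is unblinded by design. The groups differ in injection sites and in syringe counts (1–2 in Group 1; for Group 2, "Total syringes used per person will have a range of 2-5"), so a rater who knows the group could lean toward one method without intending to.

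**Working it through.** **Inputs from the protocol.** 16 patients (Study Design, Scope), randomized 1:1 (Protocol Summary), so 8 per group; JRS in whole points from 0 to 4. The protocol gives no justification for the 16, so there is no planned figure to reproduce.

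**Assumed inputs.** The protocol gives no distribution of JRS change, SD or rater correlation. All of these are assumptions, shown as ranges.

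**1. How often equal methods produce a leader.** Let S be the sum of 8 patients' reductions in one group. Then P(one group leads) = 1 − Σ P(S = s)², by exact convolution.

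Example: 10% of patients improve by 0 points and 90% by 1 point. S is binomial(8, 0.9), with leading probabilities 0.4305, 0.3826, 0.1488 and 0.0331. The sum of squares is 0.1853 + 0.1464 + 0.0221 + 0.0011 ≈ 0.355, so P(lead) = 0.645.

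| Assumed reductions (%) | SD | One group leads |
|---|---|---|
| 20/60/20 at 0/1/2 | 0.63 | 84.3% |
| 30/50/20 at 0/1/2 | 0.70 | 85.9% |
| equal thirds at 0/1/2 | 0.82 | 87.9% |
| 10/20/40/30 at 0/1/2/3 | 0.94 | 89.5% |
| 50/50 at 0/1 | 0.50 | 80.4% |
| 10/80/10 at 0/1/2 | 0.45 | 77.2% |
| 10/90 at 0/1 | 0.30 | 64.5% |
| 5/95 at 0/1 | 0.22 | 47.9% |

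**2. How often the two dermatologists point to opposite groups.** Simulation with 20/60/20 and no true difference. If the whole-point ratings themselves correlate 0.9 down to 0.3 (each rating shared with that probability), the result is about 3.5–26%. If 0.9 down to 0.3 is instead the correlation of an underlying normal score, it is about 10–28%. A continuous approximation that ignores ties gives more (14% at 0.9, 33% at 0.5), but it does not suit whole-point grades.

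**3. Illustration of rater lean.** Suppose the methods are equal at 20/60/20 and an unblinded rater credits one extra point to one in four Group 2 patients. Group 2's recorded distribution over 0/1/2/3 becomes:
- 0: 0.20×0.75 = 0.15
- 1: 0.60×0.75 + 0.20×0.25 = 0.50
- 2: 0.20×0.75 + 0.60×0.25 = 0.30
- 3: 0.20×0.25 = 0.05

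Convolution gives Group 2 the lead in 70% of trials and Group 1 in 19%, against 42% each without lean. The same calculation at one in ten gives 54% and 31%. An interval rule alone does not remove this: at one in four, false Group 2 claims rise from about 2.5% to 9.0%.

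**4. What an interval would deliver.** Half-width = t(0.975, 14 df) × SD × √(2/8) = 2.145 × SD × 0.5. Power is from the noncentral t, with noncentrality = difference / (SD × 0.5).

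| SD | Half-width | Power, true 0.5 points | Power, true 1 point |
|---|---|---|---|
| 0.5 | 0.54 | 46% | 96% |
| 0.7 | 0.75 | 27% | 76% |
| 1.0 | 1.07 | 15% | 46% |

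Simulated false claims with the t-interval are 4.5–5.4% for the first four distributions in step 1 and about 7.5% for the 50/50 split.

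**5. Why the method must be named in advance.** Take reductions of 2,2,2,1,1,1,1,1 against 1,1,1,1,1,1,0,0. The means are 1.375 and 0.75, a gap of 0.625; the pooled variance is (0.268 + 0.214)/2 = 0.241. The t-interval is 0.625 ± 2.145 × 0.491 × 0.5, or 0.10 to 1.15 (p = 0.023). Over all 12,870 allocations, the exact permutation p is 0.072 and mid-p is 0.036. One data set thus gives different verdicts.

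**6. When the t-interval collapses.** P(no variation in either group) = (Σ p⁸)². For 10/90 this is (0.9⁸ + 0.1⁸)² = 18.5%; for 5/95, 44%; for 10/80/10, about 3%. A fallback rule is needed.

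**The case against.** The strongest reply is that this is a 16-patient, single-site study and the comparison is secondary. Items 2 and 3 can be read as comparisons to be reported rater by rater, with no formal claim. That is fair as far as it goes. A reader might infer that the protocol will declare a winner on any numerical lead; the text does not say so, and the figures in step 1 hold only on that reading. What remains is that the stated objective is to determine superiority and no other rule is supplied.

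A reader might also infer that the blinded dermatologist is not masked to group. The documents do not show that. Before/after masking is stated for evaluators generally, so the contrast between a blinded and an unblinded dermatologist may well mean masking to group. The term is undefined; the masking is not shown to be absent.

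Nor does the "Blinded Physician Assessment" form show that before/after masking fails. The absolute JRS grade and the comparison with the pre-injection photograph are separate items, the extracted text of the form is garbled, and nothing says the blinded rater completes the visit fields.

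Finally, it is tempting to say that no blinded rating exists 4 weeks after a touch-up. Return Visits provides a further 1-month visit. If the retreatment schematic counts from first treatment, its 8-week column is that visit, and blinded evaluation is marked there. The column needs a clearer label; the visit is not shown to be missing.

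The size of the rater lean in step 3 is invented for illustration, and that limitation stands.

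**Conclusion.** The point holds as a gap in the decision rule: a superiority objective is tied only to a larger reduction, and an unblinded dermatologist is named beside a blinded one with no precedence. Taken literally, equal methods at 8 per group would yield a leader in about 77–90% of trials under most assumed distributions, or 48–65% if 90–95% of patients respond alike. The dermatologists would disagree on direction in roughly 4–28%. Every such figure rests on assumed distributions and correlations. The gap itself does not, since it is visible in the text. It should be corrected because it concerns the comparison in the title and can be settled before the data are seen; as a secondary objective, it does not undermine the trial as a whole.

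**What to change.** - Base Endpoint #2 on the blinded dermatologist's JRS grade, and state that this rater is masked to group.
- Report the Group 2 minus Group 1 difference in mean JRS reduction at 4 weeks after the last injection, by assigned group, with a two-sided 95% confidence interval. Name the method in advance: a t-interval, or the inversion of an exact or mid-p permutation test.
- Claim superiority only if the interval excludes zero. Otherwise give the estimate and say that the methods were not distinguished.
- If neither group shows any variation, so that a t-interval collapses, let the prespecified permutation p-value (below 0.05) decide.
- Report the unblinded dermatologist and patient comparisons separately, as supportive.
- Reconcile the retreatment schematic with the visit timing in Protocol Summary and Return Visits, so that it is clear which column falls 4 weeks after the last injection.

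The alternative is to reword the objective as descriptive: estimate the difference with its interval and make no superiority claim.

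**Cost.** Mostly wording. The blinded ratings are already scheduled, and no patients or raters are added. One rater is noisier than two. Power is low: about 15–46% for a true 0.5 points and 46–96% for 1 point, at assumed SDs of 1.0 down to 0.5. The t-interval is approximate on whole-point grades; a permutation method guards against that, and the exact version does so at some further loss of power. Masking to group may be incomplete, since "Frontal, 45- and 90-degree angle shots at standard illuminations will be taken" and cheek fullness can show in such views.
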